### **Exclusion Criteria**

Individuals were not eligible to be enrolled into the DAISY study General Population cohort if cord blood was not available for genetic screening, if other severe co-morbidities were

indicated, if parents refused consent to screening or follow-up, if at least one parent or legal guardian did not speak English or if T1D had been diagnosed.

Individuals were not eligible to be enrolled into the DAISY study Sibling/offspring cohort if they did not have a first degree relative with T1D, if other severe co-morbidities were indicated, they were older than 4 years of age (older than 7 years of age, before 1997), if parents refused consent to follow-up, if at least one parent or legal guardian did not speak English or if T1D had been diagnosed.

Individuals that do not agree to the long-term storage of data and specimen samples will be excluded.

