#### **Specific Aim 1. Determine the natural history of islet autoimmunity and to explore the heterogeneity of diabetes and other autoimmune phenotypes in young adults through follow-up of the existing cohort for 5 more years.**

We will follow already established cohort of youth at high risk of T1D and other autoimmune diseases (current n=1149, median age 17.2 y, IQR 13.5-20.2 y). We will estimate overall burden of pre-clinical and clinical T1D, celiac, thyroid, adrenal, rheumatic and parietal autoimmune disease in Colorado by age 25. This will inform future screening and prevention programs. We will further explore the apparent heterogeneity of IA and its implications for adult-onset diabetes. Selected hypotheses include:

- Hypothesis 1.1: Persistent IA triggered after the age of 6 y results in T1D diagnosis in early adulthood
- Hypothesis 1.2: Transient childhood IA does not increase the risk of diabetes in early adulthood
- Hypothesis 1.3: Sedentary life-style and insulin resistance predict faster progression from persistent IA to T1D

**Statistical Analyses and Power** Cox PH analysis will be used to test Hypothesis 1.1 and 1.2, controlling for HLA-DR,DQ, family history of T1D, sex and ethnicity. Similarly, we will estimate adjusted hazard ratios (HR) for sedentary lifestyle and insulin resistance, adjusted for Tanner Stage and diet (Hypothesis 1.3). Assuming an additional 5% of children will seroconvert, we will have 80% power at a  $\alpha=0.05$  to detect  $HR>1.8$  or  $< 0.56$  /SD.

Joint latent class models. Using fixed and time-varying covariates from the 1-year period following conversion to IA, we will develop a joint latent class model that captures the dependencies between our fixed and longitudinal covariates (age, HLA risk group, family history, BMI, glucose, physical activity, insulin resistance, development of additional IAb) and time from IA conversion to T1D. We assume that heterogeneity across our cohort can be distilled into homogeneous latent subgroups with common covariate trajectories or patterns and common risk of T1D. We will implement the method using the *lcmm* R package, which will also allow us to summarize dynamic predictive accuracy of the joint model over time.

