Analytic methods to examine age-related heterogeneity will include testing age\*exposure interaction terms with age as a continuous variable in a Cox PH model. If these are significant, suggesting violation of the assumption of proportionality, we will explore age cut-points using B-spline functions, and adjusting for variables found to be associated with IA in the previous investigation. We will then incorporate these age cut-points into the interactions terms in the proportional hazards model to test the age-related heterogeneity.

Power analysis. A two-sided log rank test with an overall sample size of 2,547 subjects (Hypotheses 1.1 and 1.2) with an overall IA rate of 9% in 15 years achieves 80% power at a 0.05 significance level to detect a HR=0.66 assuming that the proportion of children lost to follow-up is 0.20. These results are based on the assumption that the hazard rates are proportional over time. Adjusting for covariates in a Cox model and assuming that the regression of cohort membership on covariates has an R^2 of 0.5, the minimally detectable hazard ratio is 0.56. For the Hypothesis 1.3, among IA positive children (n=98), we will have 80% power to detect a hazard ratio of 1.87 for each SD increase in time spent sedentary, waist circumference, and BMI, assuming 20% of children with IA will develop T1D. Expected SDs: time spent sedentary=90 minutes/day; waist circumference=15cm; BMI=4.3 kg/m^2.

**Specific Aim 2. Validate candidate proteomic biomarkers of IA and T1D, in a nested-case study of 213 youth with persistent IA and 213 controls.**

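### The adjusted detectable hazard ratio of 0.56 for Hypotheses 1.1 and 1.2 rests on an R² of 0.5 for cohort membership that conflicts with the protocol's own covariates and entry criteria, and cohort membership is not the exposure either hypothesis tests

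*Protocol*

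**What the plan says.** The figure is in Section IV.F (Data Analysis Plan), Specific Aim 1, in the paragraph on power analysis. The unadjusted calculation takes "A two-sided log rank test with an overall sample size of 2,547 subjects (Hypotheses 1.1 and 1.2") as its starting point. The event rate enters separately, "with an overall IA rate of 9% in 15 years". On that basis the design "achieves 80% power at a 0.05 significance level to detect a HR=0.66". Losses are allowed for by "assuming that the proportion of children lost to follow-up is 0.20". The adjusted calculation is then made "assuming that the regression of cohort membership on covariates has an" R² whose value is put at 0.5. Its conclusion is that "the minimally detectable hazard ratio is 0.56".

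The covariates are set in the same section, under Statistical Analyses and Power. Hypotheses 1.1 and 1.2 are to be tested by Cox regression "controlling for HLA-DR,DQ, family history of T1D, sex and ethnicity".

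Four other places bear on this:

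- **Research Plan, Specific Aim 1, Study Population** names two cohorts: 1,424 general-population newborns chosen on HLA genotype, and 1,123 relatives of patients with T1D enrolled whatever their HLA genotype.
- **Section IV.B, Exclusion Criteria** makes children ineligible for the sibling/offspring cohort "if they did not have a first degree relative with T1D".
- **Section IV.B, Current Study Population** gives non-Hispanic white shares of 56% in the newborn cohort and 85% in the sibling/offspring cohort.
- **Section IV.D, the quality-control text on islet autoantibodies** says the two cohorts will not be pooled for analysis.

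A bound of 0.56 per SD also appears under Statistical Analyses and Power. It is a different statement and is not reviewed here.

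**The concern.** The R² in this calculation is the share of variation in the tested variable that the other covariates explain. The effective number of events shrinks by 1 − R², so the detectable HR depends heavily on it.

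If the tested variable is cohort membership, one listed covariate, family history of T1D, is positive by definition for everyone in one cohort. It should be uncommon in the other, which Section II describes as children without diabetic relatives. The two variables then nearly coincide, and an R² of 0.5 is hard to defend. The protocol gives no basis for it.

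The paragraph is also attached to hypotheses about something else. Hypothesis 1.1 concerns persistent IA arising after age 6, and Hypothesis 1.2 concerns transient childhood IA. At stake is whether a reader can rely on 0.56 as the sensitivity of these analyses.

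**Working it through.** **Inputs.** From the protocol: N = 2,547; IA rate 9%; loss 20%; two-sided α = 0.05; power 80%; R² = 0.5; cohort sizes n₁ = 1,123 (relatives) and n₀ = 1,424 (newborns). Not in the protocol: f, the share of newborns with a first-degree relative with T1D. It is varied below as an assumption.

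**Step 1: which contrast.** 1,424 + 1,123 = 2,547, exactly the sample size in the power paragraph. These are the only two cohorts in the document that give that total.

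**Step 2: reproduce the stated figures.** Events D = 2,547 × 0.09 × 0.80 = 183.4. With Schoenfeld's formula, detectable HR = exp(−(1.960 + 0.842) / √(D·p·(1−p))):

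- p = 0.5 gives 0.661; p = 1,123/2,547 = 0.441 gives 0.659. Both round to the stated 0.66.
- With R² = 0.5, exp(ln 0.66 / √0.5) = 0.556, which rounds to the stated 0.56.

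The arithmetic is right. It cannot show which contrast was meant, because an equal split and a 44:56 split both give 0.66. That reading rests on the wording and on the sample size.

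**Step 3: R² from family history alone.** All n₁ relatives are positive, as are f·n₀ newborns. For this 2×2 table

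R² = φ² = n₁(1 − f) / (n₁ + f·n₀).

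Setting R² = 0.5 gives f = 0.5·n₁ / (n₁ + 0.5·n₀) = 561.5 / 1,835 = 0.306, or about 31%.

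**Step 4: consequence.** Detectable HR = exp(ln 0.66 / √(1 − R²)). Power at HR 0.56 = Φ(|ln 0.56|·√(D·p·(1−p)·(1−R²)) − 1.96), with p = 0.441.

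| Assumed f | R² | Detectable HR | Power at HR 0.56 |
|---|---|---|---|
| 1% | 0.98 | 0.06 | 8% |
| 2% | 0.96 | 0.14 | 13% |
| 5% | 0.89 | 0.28 | 25% |
| 10% | 0.80 | 0.40 | 42% |
| 31% | 0.50 | 0.56 | 79% |

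Worked line for f = 10%: R² = 1,123 × 0.90 / (1,123 + 142.4) = 1,010.7 / 1,265.4 = 0.80; √(1 − R²) = 0.449; exp(−0.4155 / 0.449) = 0.40.

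For scale, Section IV.D (Benefits) puts T1D at 0.5–1% of the U.S. population. Assuming three first-degree relatives per child, f is about 1.5–3%, R² about 0.97–0.93 and the detectable HR about 0.10–0.20.

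Adding HLA, sex and ethnicity cannot lower R². HLA selection and ethnicity both differ between the cohorts.

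**Step 5: compare with the hypotheses.** Neither hypothesis has cohort membership as its exposure. The analysis plan uses family history as an adjuster and lists no cohort coefficient to be tested, and Section IV.D says the cohorts will not be pooled. The powered contrast is therefore not the planned one.

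**The case against.** The strongest reply is that no planned result depends on this R². The Cox models test late and transient IA, so family history cannot make a planned cohort coefficient unidentifiable when none is planned. This stands. A reader might infer that the planned models are nearly unidentifiable, or that a null result would be wrongly taken to exclude HR 0.56 between cohorts. The documents do not support either inference.

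Nor does the collinearity carry over to the exposures actually tested. Section III reports a sibling with T1D in 27% of 143 early-onset and 12% of 65 late-onset IA cases (cut at age 7). For that table φ² ≈ 0.15² × (0.3125 × 0.6875) / (0.223 × 0.777) ≈ 0.03. It covers siblings only and uses a slightly different age cut, but it is far from 1.

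A reader might also take R² close to 1 as established. It is not: f is not reported, the newborn criteria do not exclude children with diabetic relatives, and selection on HLA could raise f above what population prevalence suggests. The lowest HRs also stretch a large-sample formula; at f = 1% only about 14 children separate the two variables.

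Finally, cohort membership might have been loose wording for an IA exposure group, in which case the R² argument falls away. The text does not say so, and the paragraph would then misname its contrast and still need rewriting.

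What remains is that the sentence as written conflicts with the covariate list and the entry criteria, and does not power the stated hypotheses.

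**Conclusion.** Wrong as written, of moderate severity. The error is in an input assumption, not in the arithmetic.

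On the literal reading, R² = 0.5 would need about 31% of the newborns to have a first-degree relative with T1D. For an assumed share of 1% to 10%, R² from family history alone is about 0.98 to 0.80, the detectable HR about 0.06 to 0.40, and power at 0.56 about 8% to 42%. The exact values depend on f. The direction does not: any f below about 31% makes 0.56 too favourable for that contrast.

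Whichever contrast was meant, 0.56 does not describe the power of the planned tests of Hypotheses 1.1 and 1.2. The severity is moderate because the cohort is already enrolled and the correction changes no planned model or estimate.

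**What to change.** Delete the sentence that derives 0.56 from an R² of 0.5 for cohort membership. In its place:

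1. Name the exposure that each of Hypotheses 1.1 and 1.2 tests.
2. Regress that exposure on HLA-DR,DQ, family history, sex and ethnicity in the existing records, and report the R².
3. Restate the detectable HR for that exposure, using its actual group sizes.
4. If a comparison of the two cohorts is really intended, do not adjust it for family history, say that the two variables largely coincide, and reconcile it with the statement in Section IV.D that the cohorts will not be combined.

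The cost is a short regression per exposure on data already held and a change of wording. No new data are needed. The stated detectable HR may become less favourable.

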**APPROACH: Preliminary studies** DAISY added measurement of waist circumference and physical activity questionnaire at each visit starting in June 2010; these measurements are available on 1,090 subjects. Pubertal stage has been determined based on self-reported Tanner Stage at each visit. In 2011, we began collecting objective physical activity data using an accelerometer - a small device worn on the hip or lower back to measure change in velocity over time - worn for 7 days. We have identified 126 antibody positive subjects as eligible for this more intensive measurement of physical activity. We have obtained accelerometer data for 82 subjects, 69 of which have worn the accelerometer more than once; 8 have later developed T1D. We have also obtained accelerometer data one time on 55 antibody negative controls. Multivariate linear regression analysis, adjusted for age, sex, BMI, and total time recorded has shown that IA subjects spent a higher percentage of time sedentary than controls (p=0.045), less time engaged in vigorous physical activity (p=0.01), and took fewer total steps (p=0.02) and steps per minute (p=0.03). In a cross-sectional analysis, these differences translated into IA subjects spending over 110 extra minutes sedentary and 70 fewer minutes engaged in vigorous physical activity per week, compared to controls. In March of 2020 DAISY stopped offering accelerometers to participants that are antibody positive or are antibody negative controls.

**Prospective dietary data** We will continue to measure dietary intake of macronutrients, glycemic index and added sugars using a validated Youth/Adolescent Questionnaire completed by both parents and child between ages 10-12 and by the participant after age 12 on the entire DAISY cohort. In the IA positive subjects and the controls,

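### The Hypothesis 1.3 power figure (HR 1.87 per SD) is for an unadjusted model although adjustment is planned, and neither its sample for sedentary time nor the neighbouring HR 1.8 sentence is reconciled with it

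*Protocol*

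**What the plan says.** Three places in the Protocol bear on the power for Hypothesis 1.3.

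- **Section IV.F, Specific Aim 1, Power analysis.** The claim is that "among IA positive children (n=98), we will have 80% power to detect a hazard ratio of 1.87 for each SD increase". It covers three exposures, "for each SD increase in time spent sedentary, waist circumference, and BMI", and rests on "assuming 20% of children with IA will develop T1D". The scale is given as "Expected SDs: time spent sedentary=90 minutes/day; waist circumference=15cm". The sentence just before it, on Hypotheses 1.1 and 1.2, moves the detectable HR from 0.66 to 0.56 by assuming an R-squared of 0.5 for the regression of cohort membership on covariates. No such step is taken for Hypothesis 1.3.
- **Section IV.F, Specific Aim 1, Statistical Analyses and Power.** The planned hazard ratios are "adjusted for Tanner Stage and diet (Hypothesis 1.3"). The next sentence reads "Assuming an additional 5% of children will seroconvert, we will have 80% power" and goes on to HR above 1.8 or below 0.56 per SD. It names no hypothesis, sample size or event count.
- **Research Plan, Hypothesis 1.3, Preliminary studies.** Of 126 antibody-positive subjects eligible for accelerometry, "We have obtained accelerometer data for 82 subjects, 69 of which have worn the accelerometer more than once; 8 have later developed T1D". The paragraph ends: "In March of 2020 DAISY stopped offering accelerometers to participants that are antibody positive". It also describes waist circumference and a physical activity questionnaire, available on 1,090 subjects.

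**The concern.** The power figure should describe the model that will be fitted. Adjusting for covariates correlated with the exposure inflates the variance of its coefficient. Tanner Stage and diet can be expected to correlate to some degree with sedentary time, waist and BMI. If 1.87 ignores this, a null adjusted result would be read against a claimed 80% power that the analysis does not have.

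Two further items make the claim hard to rely on. The 98 children exceed the 82 with reported accelerometer data, and the devices are no longer offered. The 1.8/0.56 sentence sits directly after the Hypothesis 1.3 model and is expressed per SD, so it looks like a second power figure for the same hypothesis, with nothing to reconcile it with 1.87.

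**Working it through.** **Inputs from the Protocol:** n = 98; 20% T1D; 80% power; alpha 0.05; HR 1.87 per SD; 82 accelerometer wearers; for Hypotheses 1.1/1.2, N = 2,547, IA rate 9%, 20% lost, R-squared 0.5. **Assumed:** a two-sided test for Hypothesis 1.3 (stated only for 1.1/1.2), equal groups for 1.1/1.2, and every R-squared used for 1.3.

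**Formulas** (Cox model, continuous covariate, HR per SD):
- Events needed: D = (1.960 + 0.842)² / [(ln HR)² (1 − R²)] = 7.849 / [(ln HR)² (1 − R²)]
- Detectable HR: exp{2.802 / √[D(1 − R²)]}
- Power: Φ{√[D(1 − R²)] · ln HR − 1.960}

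**1. Reproduce 1.87.** With R² = 0, D = 7.849 / (ln 1.87)² = 20.0, so N = 20.0 / 0.20 = 100.2. The plan has 98 × 0.20 = 19.6 events, which gives a detectable HR of 1.88 and 79% power at 1.87; 20 events gives 1.87. The stated figure therefore reproduces at R² = 0. A one-sided test would need only 79 children, and taking off 20% loss would give HR 2.03; neither fits.

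**2. Allow for the planned adjustment (19.6 events).**

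| Assumed R² | Detectable HR | Power at 1.87 | N for 80% power at 1.87 |
|---|---|---|---|
| 0 | 1.88 | 79% | 101 |
| 0.1 | 1.95 | 75% | 112 |
| 0.2 | 2.03 | 70% | 126 |
| 0.3 | 2.13 | 64% | 144 |
| 0.5 | 2.45 | 50% | 201 |

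**3. Sedentary time on the 82 reported wearers.** 82 × 0.20 = 16.4 events. The detectable HR is 2.00 at R² = 0 (power at 1.87 about 72%), 2.17 at R² = 0.2 and 2.66 at R² = 0.5.

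**4. Where 1.8/0.56 comes from.**
- As a Hypothesis 1.3 figure, HR 1.8 needs 7.849 / (ln 1.8)² = 22.7 events, or about 114 children at 20%.
- Adding 5% to 98 gives 102.9 children, 20.6 events and HR 1.85.
- Adding 5% of the 1,149 in follow-up gives about 155 children and HR 1.65. Adding 5% of the 1,149 − 126 = 1,023 not counted as antibody positive gives about 149 children, 29.8 events and HR 1.67.
- For Hypotheses 1.1/1.2, 2,547 × 0.8 × 0.09 = 183.4 events, and exp(−2 × 2.802 / √183.4) = 0.66, as stated. With R² = 0.5, 0.66^(1/√0.5) = 0.556, as stated (0.56), and 1 / 0.556 = 1.80.

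The pair 0.56/1.8 therefore matches the adjusted result for Hypotheses 1.1/1.2. That is a two-group comparison, to which a per-SD label does not apply.

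**The case against.** Several stronger readings are tempting, and the Protocol does not support them.

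- **That the sedentary-time power can never be reached.** Only accelerometer wear stopped; follow-up for T1D continues, and power depends on events. Unadjusted, 20.0 events is 24% of 82 wearers. The count of 82 is undated and sits under preliminary studies in text with other counts from 2015, so the final number may be higher; 126 subjects were eligible.
- **That the T1D rate is really 10%.** The 8 diagnoses among 82 wearers are an interim count, while 20% is a projection. Elsewhere (Specific Aim 2, Approach) 89 of 213 persistent IA cases, 42%, already had T1D.
- **That 1.8 and 1.87 contradict each other.** The two sentences use different assumptions, and the first may not concern Hypothesis 1.3. If about 149 children were meant, power at HR 1.8 would be about 89%, and an R-squared near 0.24 would give exactly 1.8. The figure is unattributed and unreconciled; it is not a proven contradiction.
- **That R-squared 0.5 should simply be carried over.** It was specified for cohort membership, and the planned covariates there include family history, which helps define the cohorts. Nothing shows that Tanner Stage and diet explain half the variance of these exposures. It is only the upper end of an illustrative range.
- **That 98 accelerometer records are assumed.** The power text says only sedentary time, and a questionnaire also exists. Minutes per day makes accelerometry likely, but this is an inference. Waist and BMI are unaffected by it.

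It is also fair to say that this is an observational follow-up of an existing cohort, where these figures set no enrolment target. What stands against all of this is that any R-squared above zero makes 1.87 optimistic for the planned model, for all three exposures.

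**Conclusion.** The point holds in a limited form. The stated 80% power at HR 1.87 belongs to an unadjusted model, not to the planned one. With 98 children and 20% T1D, modest adjustment (R-squared 0.1 to 0.3) moves the detectable HR to about 1.95 to 2.13 and power at 1.87 to 75% to 64%; at 0.5 the values are 2.45 and 50%. These depend on R-squared values that the Protocol does not supply.

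For sedentary time, 82 wearers at 20% T1D give about 2.00 unadjusted and 2.17 at R-squared 0.2. This is conditional on accelerometry being the source and on the reported count and the 20% rate being final.

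The 1.8/0.56 sentence is either mislabelled (the adjusted Hypotheses 1.1/1.2 result with a wrong /SD) or, on the readings of the 5% seroconversion assumption tried here, does not reproduce for Hypothesis 1.3.

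**What to change.** In section IV.F, give a single power statement for Hypothesis 1.3 that:

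- refers to the model adjusted for Tanner Stage and diet, with a stated and justified R-squared, or a range;
- gives the actual n and expected T1D events for each exposure: final accelerometer wearers for sedentary time if that is the source, and IA-positive children with measurements for waist and BMI;
- names the source of sedentary time.

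Then attribute the 1.8/0.56 sentence to the hypothesis it belongs to and correct its units, or remove it. No change of primary exposure measure is required; whether to favour the questionnaire is the investigators' choice.

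The cost is a few sentences, a count from the existing database and a less favourable detectable HR. No new data are needed.
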